Participants will be randomly allocated to in-person CBT-I or iCBT-I or WL. Randomization will be determined using an online research randomization tool (27), which is not predictable and eliminates potential experimenter bias (28). Forty-five participants will be enrolled in the pilot RCT, with 15 randomized into each study group. A staff member who is not associated with the study will conduct the randomization and sequence generation and will put each participant assignment into opaque envelopes that contain the results of the randomization. After a baseline assessment is completed a study therapist will open an envelope and inform participants of their assignment.

Participants randomized to in-person or online treatment will be invited to participate in 6 sessions of CBT-I. Participants randomized to the waitlist group, will receive a pamphlet with information about community resources for pregnant women.

Week 2- Week 7: If randomized to the in-person treatment group, participants will be invited to attend 6 in-person sessions of cognitive-behavioural therapy for insomnia, which will take place at the University of Calgary in a newly renovated research space (*see Appendix A for the structure of each session*). Additionally, they will receive a manual which will include weekly readings relevant to the material being taught in the sessions and an informational pamphlet with helpful community resources for pregnant women. During this intervention, they will become familiarized with self-management approach for insomnia, sleep basics and sleep restriction, stimulus control, problem solving to cope with sleep disturbances and relapse prevention.

Participants randomized to online cognitive behavioural treatment (iCBT-I) will complete a series of 6 modules, where the main learning components are included in video and audio materials. To log onto the CBT-I intervention website, participants will be given login information through an anonymized email address, which will be used only for the duration of the study. Like the in-person intervention, the iCBT-I intervention includes instruction and homework on sleep hygiene and relaxation strategies. Participants will be contacted regularly by a member of the study team to ensure that there are no issues with accessing online readings and audio/visual materials (29).

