The primary response variable, change in symptoms on the Insomnia Severity Index (ISI) between baseline (T2) and post treatment follow-up (T2), will be analyzed with using Repeated Measures Analysis of Variance (ANOVA) with a linear distribution specified at a significance level of $\alpha = 0.05$. Using data from our pilot study, and insomnia symptoms on the ISI, we found that pre-post treatment yielded a $d = 3.07$. Prior studies of CBT-I for patients with insomnia have found large between-group effect sizes in a range from $d = 1.1$ to $d = 1.6$, even in patients with comorbid mental illness; however, we completed our power calculations using a more conservative effect size estimate, which showed that 18 patients are required to have a 95% chance of detecting a between-group effect size of $d = 0.8$ at a significance level of $\alpha = 0.05$ on the ISI. Although we had no attrition from our pilot study, we added a potential attrition rate of 20%, resulting in 14 participants to detect group differences in our pilot RCT.

Based on previous research, we do not expect to see differences in iCBT-I versus in person CBT-I; however, we expect that both conditions will outperform the WL group. Although we had no attrition from our pilot study, we calculated a potential attrition rate of 20% based on previous research in this area, resulting in 45 participants in our pilot RCT. Across 3 arms, this will allow 14 participants in each group and will provide a power of more than 90% to detect a difference of 8 points on the ISI, which is indicative of a clinically significant change (30).

Primary Aims

Hypothesis 1) Participants who receive in-person and online CBT-I (versus WL) will report fewer insomnia symptoms as measured by Insomnia Severity Index (ISI) at the post treatment assessment point (T2).

Primary aims will be assessed using Generalized Estimated Equations (GEE) and an intent-to-treat (ITT) basis, including data for each participant who was randomized, regardless of their

adherence to the intervention or whether they withdraw from the study. Analyses including only patients fulfilling the treatment will also be conducted.

Secondary Aims

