Hypothesis 2.1) Participants who receive in-person and online CBT-I (versus WL) will experience fewer symptoms of depression as assessed by the Edinburgh Postpartum Depression Scale (EPDS) and will be less likely to be diagnosed with depression as assessed using Structured Clinical Interview for the DSM-IV (SCID) at T2.

Hypothesis 2.2) Participants who receive online and in-person CBT-I (versus WL) will be less likely to be diagnosed with insomnia, as measured by the Insomnia Interview Schedule (21), at T2.

Hypothesis 2.3) Participants who receive in-person and online CBT-I (versus WL) will experience better objective sleep as assessed by actigraphy (higher sleep efficiency and lower sleep onset latency) at T2.

Secondary aims including changes in actigraphy parameters, diagnosis of insomnia, symptoms of and diagnoses of depression will be examined. Changes in binary outcomes will be tested using Generalized Estimated Equations (GEE) with a binary outcome specified.

RESEARCH MANAGEMENT

[name], as the Primary Investigator will be responsible for the overall management of the project. She received extensive training in cognitive behavioral interventions and will be responsible for training clinical psychology master's students in the delivery of in-person cognitive behavioural therapy for insomnia adapted for pregnant women. [name] is an experienced clinician and will provide clinical support regarding the establishment of therapy protocols and ongoing consultation regarding fidelity to the CBT treatment protocol. [name] will be responsible for supervising master's students in administering diagnostic interviews for Axis I mood disorders. [name] will be responsible for supervising the research assistant at the University of Manitoba who will be coordinating the online portion of the intervention.

RESEARCH ENVIRONMENT

All assessments and in-person CBT-I sessions will take place at the University of Calgary in a newly renovated research space designed specifically for conducting and evaluating evidence-based interventions which is located in suite 292 of the Education Classroom Building.

REFERENCES

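### The ISI endpoint is given two analyses, repeated measures ANOVA and intent-to-treat GEE; the headings point to GEE, but no sentence ranks them and the GEE's small-sample inference is not specified

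*Combined protocol and SAP*

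**What the plan says.** Two sections of the Analysis Plan assign a method to the ISI.

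- **Sample Size Power Calculation.** The primary response variable, ISI change from baseline to post-treatment, "will be analyzed with using Repeated Measures Analysis of Variance (ANOVA) with a linear distribution specified" at a 0.05 significance level.
- **Primary Aims.** Directly below Hypothesis 1 (ISI at T2): "Primary aims will be assessed using Generalized Estimated Equations (GEE) and an intent-to-treat (ITT) basis". The sentence goes on to include every randomised woman whatever her "adherence to the intervention or whether they withdraw from the study".

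One analysis is marked as additional, and it is not the ANOVA: "Analyses including only patients fulfilling the treatment will also be conducted". The only other GEE sentence, under Secondary Aims, concerns binary outcomes: "Changes in binary outcomes will be tested using Generalized Estimated Equations (GEE) with a binary outcome specified". Neither section gives a working correlation, variance estimator, small-sample correction or reference distribution.

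On size, Procedures states: "Forty-five participants will be enrolled in the pilot RCT, with 15 randomized into each study group". On losses, the sample size section states: "we calculated a potential attrition rate of 20% based on previous research in this area".

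**The concern.** The ANOVA sentence is worded as the analysis of the primary variable, not as the model behind the power figure. Read literally, the endpoint has two analyses, and they do not use the same women once T2 values are missing. A standard repeated measures ANOVA needs both visits, whereas the GEE sentence covers withdrawals. The result that decides Hypothesis 1 should be fixed in writing before data are seen.

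A second, separate gap remains even if GEE is accepted as primary. With about 45 clusters, the GEE p-value depends on the variance estimator and reference distribution, and the plan names neither.

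**Working it through.** **Inputs from the documents.** 3 arms of 15; 20% attrition; alpha 0.05; d = 0.8 from the power calculation. The plan also reports that prior studies "have found large between-group effect sizes in a range from" d = 1.1 to d = 1.6. The plan gives no figure for the behaviour of either test, so there is none to reproduce.

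**Assumptions not in the documents.** T1-T2 correlation 0.3, 0.5 or 0.7; normal outcomes with equal SDs; T2 missing purely by chance; two-sided tests; one active arm versus waitlist (WL).

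**Step 1: who is analysed.** 0.20 × 45 = 9 women without T2. A standard ANOVA keeps 45 − 9 = 36, or 12 per arm; the GEE keeps all 45.

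**Step 2: complete data, by hand.** With two visits and a full arm-by-time mean, both methods estimate the difference in mean change, so the point estimates are equal. With n per arm, the two-arm ANOVA variance is SS/[n(n−1)], where SS is the within-arm sum of squares of change. The uncorrected sandwich variance is SS/n², smaller by the factor (n−1)/n. Sandwich-z therefore rejects when |t| > 1.96 × √((n−1)/n), with t on 2n−2 df.

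| n per arm | Effective cut-off | Correct t cut-off | True level | Interval width ratio |
|---|---|---|---|---|
| 12 | 1.877 | 2.074 | 7.4% | 0.905 |
| 14 | 1.889 | 2.056 | 7.0% | 0.919 |
| 15 | 1.894 | 2.048 | 6.9% | 0.924 |

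Simulation (200,000 replicates) gave 7.33%, 6.99% and 6.87%. Kauermann-Carroll variance with t gave 4.95-5.06%, and Mancl-DeRouen with t gave 4.10-4.36%. Contrasting both CBT-I arms with WL changes little: uncorrected GEE rejects 6.8% at 15 per arm and 7.3% at 12.

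**Step 3: 20% of T2 missing, simulated** (n = 15 per arm; 100,000 null replicates, 60,000 otherwise). ANOVA here is a t test on change in women with both visits in the two arms. Three entries are for correlation 0.3/0.5/0.7.

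Disagreement between ANOVA and GEE on p<0.05:

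| GEE | d = 0.8 | d = 1.1 | d = 1.6 |
|---|---|---|---|
| Exchangeable, sandwich-z | 11.2/10.5/8.2% | 11.9/8.8/3.7% | 6.0/2.3/0.2% |
| Exchangeable, Kauermann-Carroll t | 7.7/6.6/4.4% | 8.6/5.8/2.1% | 4.5/1.6/0.1% |

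Independence GEE disagrees more often at d = 0.8: 13.9-16.7% (sandwich-z) or 11.5-17.5% (corrected). With a three-arm pooled ANOVA error at d = 0.8, the exchangeable figures are 11.5/10.6/7.9% and 9.1/8.5/6.5%.

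Type I error:

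| Analysis | Rejection rate under the null |
|---|---|
| ANOVA alone | 5.0% |
| Exchangeable GEE, sandwich-z, alone | 7.4/7.4/7.4% |
| Either of these two | 7.9/7.7/7.5% |
| Independence GEE, sandwich-z, alone | 7.0/6.9/6.6% |
| Either this or ANOVA | 8.3/8.5/8.7% |
| Exchangeable GEE, Kauermann-Carroll t, alone | 5.1/5.0/5.0% |
| Either this or ANOVA | 6.1/5.9/5.6% |

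Over uncorrected GEE alone, freedom to choose adds 0.1-0.5 points (7.5 − 7.4 to 7.9 − 7.4) with exchangeable correlation, and 1.3-2.1 points (8.3 − 7.0 to 8.7 − 6.6) with independence. Over the corrected exchangeable GEE it adds 0.6-1.0 points.

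Repeat runs at correlation 0.5 gave 4.7-5.1% for ANOVA, 7.0-7.4% for sandwich-z and 4.8-5.1% for Kauermann-Carroll with t. Disagreement at d = 0.8 was 10.4-10.8% uncorrected and 6.7-6.9% corrected.

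**Step 4: power at d = 0.8, 20% missing.**

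| Analysis | Power |
|---|---|
| Exchangeable sandwich-z | 44.1/55.5/74.4% |
| Exchangeable Kauermann-Carroll t | 37.1/48.0/67.8% |
| ANOVA, two-arm error | 35.1/46.2/66.8% |
| ANOVA, three-arm pooled error | 35.7/47.1/68.3% |

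**The case against.** The structure largely answers the first question. The ANOVA sentence sits under the power calculation and leads straight into effect sizes and patient numbers; the GEE sentence sits under Primary Aims, just below the hypothesis it tests. The odd phrase about a linear distribution resembles the later one about a binary outcome, so the authors may be naming one modelling framework loosely. This stands as far as it goes: a reader who concludes that the decisive p-value cannot be identified goes too far, because GEE can be inferred. What remains is that the text does not say it, and the two methods treat women without T2 differently.

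A reader might also infer that the plan's test runs at 7%. The documents do not support that. They name no software, variance estimator or reference distribution, so the figure is conditional on an uncorrected sandwich-z analysis that the plan neither names nor excludes.

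Nor is the choice between methods a large source of false positives: the plan's silence on ranking costs far less than an uncorrected variance would. Disagreement is highest where power is moderate and borderline results are common; at d = 1.6 it is small.

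Finally, the choice among valid small-sample corrections is partly preference. Kauermann-Carroll is not offered in every package, and corrected GEE has no clear power advantage over a pooled three-arm ANOVA.

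**Conclusion.** The point holds as a conflict between two stated rules that is cheap to remove, plus a gap in the GEE specification. It does not undermine the trial.

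- **Conflict.** A standard ANOVA leaves out about 9 of 45 women whom the intent-to-treat sentence includes. The two tests differ on significance in roughly 4-11% of trials at d = 0.8 with exchangeable GEE.
- **Type I error from choosing.** Small: 0.1-0.5 points (exchangeable) or 1.3-2.1 points (independence) over uncorrected GEE alone.
- **Unspecified inference.** About 7% instead of 5% with 12-15 women per arm, only if the uncorrected sandwich and z are used.

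The simulated figures rest on the assumed correlations, normality and missingness by chance. The complete-data levels for a single contrast follow by hand and do not depend on the correlation.

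A reader might go further and infer that the ANOVA would be biased by dropout. That can be constructed: if dropout rises with baseline ISI in the active arms only (assumed odds ratio 3.3 per SD), the ANOVA understates benefit by 0.06-0.14 SD. If WL follows the same dropout rule, the bias is within 0.001 SD. The documents give no basis for either pattern, so this is illustration and carries no weight here.

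**What to change.** In the Analysis Plan:

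1. State that the intent-to-treat GEE is the primary analysis of the ISI.
2. Delete the ANOVA clause from the sample size section, or label it a sensitivity analysis in women with both visits. That set is not the same as the treatment completers already described.
3. Add one line on inference: exchangeable working correlation; Kauermann-Carroll corrected variance, or Mancl-DeRouen where that is what the software offers (slightly conservative, 4.1-4.4%); and a t reference, for example with df equal to the women with T2 in the two compared arms minus 2. A mixed model with Kenward-Roger degrees of freedom is an acceptable alternative.

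**Cost.** A few sentences and a check that the chosen package supports the correction; no change to data collection or sample size. Intervals are about 8-11% wider than uncorrected GEE would report (1/0.924 = 1.08; 1/0.904 = 1.11). Apparent power at d = 0.8 falls about 7 points (44.1 − 37.1 = 7.0; 55.5 − 48.0 = 7.5; 74.4 − 67.8 = 6.6), because the uncorrected test is too liberal. Power is about equal to that of the ANOVA.

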Cambridge Hopkins Questionnaire for Restless Legs Syndrome	Validated, self-report assessment of restless legs syndrome. Includes questions designed to exclude common health issues that are similar to RLS symptomatology [51].	High specificity (94.4%) and sensitivity (87.2%) [51]. Previously used among pregnant women with good predictive value [75].
STOP Questionnaire	The 4-item measure includes questions about snoring, tiredness during the day, stopped breathing during sleep time, and hypertension [52].	Varied sensitivity of 76-96%, good negative predictive value among moderate to severe obstructive-sleep-apnea [52]. Used in previous research with pregnant women with great predictive value during last two trimesters [76].
Pittsburgh Sleep Quality Index	Used to assess sleep quality during previous month. 19 self-rated items, 5 questions rated by roommate or bed partner. Seven components: subjective sleep quality, sleep latency, sleep duration, habitual sleep efficiency, sleep disturbances, use of sleeping medications, daytime dysfunction. Score > 5 suggests bad sleep quality [26].	Excellent internal consistency (Cronbach α of 0.90 and 0.91). 86.1% sensitivity and 87.7% specificity for a cut-off score of 10. Validity confirmed by polysomnographic findings and sensitivity in discriminating patients from controls. Diagnostic sensitivity of 89.6% and specificity of 86.5% [26].

Multidimensional Fatigue Symptom Inventory-Short Form	30-item short form version of MFSI consists only empirically derived subscales, designed to assess general, physical, emotional and mental manifestations of fatigue [77].	Acceptable psychometric properties, can be safely used as substitute for the 83-item original version. Validity confirmed by correlation coefficient with relevant instruments (-0.21 to 0.82, p<.001), [77].
Dysfunctional Beliefs and Attitudes about Sleep Questionnaire	Cognitive scale used for assessing problematic levels of unhelpful beliefs about sleep. 16 items, 10-point Likert scale ranges from 0 (Strongly Disagree) to 10 (Strongly Agree). Captures four factors: perceived consequences of insomnia, worry/helplessness about insomnia, sleep expectations, and medication [78].	Total scores correlate with insomnia severity, anxiety, and depression, as measured by ISI and Beck Depression and Anxiety Measures, with adequate temporal stability (r=0.83) [78].
Sleep Self-Efficacy Scale	9-item scale used for measuring one's level of confidence in carrying out specific sleep-related behaviors [79].	Has been found to predict response to CBT treatment for insomnia [80, 81].
Sleep Hygiene Index	13-item self-report items used for assessing presence of behaviors thought to compromise sleep hygiene. Assesses how frequently behaviors engaged in (always, frequently, sometimes, rarely, never). Higher total scores indicative of more maladaptive sleep hygiene status [82].	Adequate reliability (Cronbach's α of 0.66); superior to previously published sleep hygiene instruments. Good validity - positively correlated with the Epworth Sleepiness Scale {r(269)=0.244, p<0.01} and the Pittsburgh Sleep Quality Index total score (r(269)=0.481, p<0.01) [82].
Pre-Sleep Arousal Scale	16-item self-report measure assessing two subscales of pre-sleep somatic and cognitive arousal. Five-point Likert scale (1, "not at all" to 5, "extremely") used to rate extent to which each item is experienced [83].	Adequate internal consistency α (α = .76 and .81 for somatic and cognitive scales, respectively), and elevated PSAS scores associated with sleep onset difficulties [83].
Glasgow Sleep Effort Scale	Measure of sleep-related effort. Example of an item: "I put off going to bed at night for fear of not being able to sleep" (Very much/To some extent/Not at all) [84].	Cronbach's α of 0.77, can discriminate between insomnia patients and "good sleepers". Good predictive value of presence of insomnia [84].

Sleep-Related Behaviors Questionnaire	Designed to assess use of safety behaviours to promote sleep and cope with tiredness, which are associated with impairment in sleep and daytime functioning. Scale will help determine effectiveness of treatment in reducing the use of unhelpful safety behaviours [85].	Good internal consistency, able to discriminate normal sleepers from those with insomnia [85].
Epworth Sleepiness Scale	It is a self-report 8-item questionnaire producing scores from 0 to 24. The scale is designed to assess the tendency to fall asleep in situations such as while working or driving. Scores greater than 10 suggest significant daytime sleepiness [86].	The Epworth Sleepiness Scale has good psychometric properties [86] correlates with objective measures of sleepiness, and has been shown to differentiate between individuals with and without sleep disorders [87].
Edinburgh Postnatal Depression Scale	Useful in identifying women at risk for depression. Scale items assess depressive symptoms including sleep disturbance, low energy and suicidal ideation [59].	Sensitivity and specificity varies by cut score, however, established as useful tool in field of perinatal mental health [88].
Generalized Anxiety Disorder	Brief measure for assessing symptoms of generalized anxiety disorder. Cut scores of 5, 10 and 15 considered to reflect mild, moderate and severe anxiety [89].	In perinatal research, sensitivity of 61.3% and specificity of 72.7% at cut score of 13. Researchers deemed scale useful in detecting perinatal anxiety symptomatology [90].
Couple Satisfaction Index	The CSI-16 scale will be administered to assess participants' relationship satisfaction. Consists of 16 six-point Likert Scale statements [91]	In comparison with relevant instruments, has higher precision of assessment, superior sensitivity for detecting satisfaction differences. Strong convergent and construct validity, Cronbach's α of .98 [91].
Big Five Inventory	Used for assessing five broad dimensions of personality traits (openness, conscientiousness, extraversion, agreeableness, neuroticism). Includes 44 five-point Likert scale items [92].	Review demonstrates good reliability and acceptable discriminant and convergent validity across several studies [92].

Actigraphy	
Provides objective information on circadian rhythm amplitude, acrophase, and mesor as well as indices of sleep efficiency, sleep latency, total sleep time, and number and frequency of awakenings. Less costly and intrusive than polysomnography (gold standard in sleep measurement)
	
Satisfactory accuracy (high sensitivity, low specificity), recommended as reliable and useful method for assessment of sleep (de Souza et al., 2003). Actigraphic estimates for sleep percentage and sleep latency correlated 0.82 and 0.90 ($p<.0001$) compared to polysomnography [93].

------------	--	--
